6. Be sure to submit **data collection instruments** for review with your e-IRB Application (e.g., measures, questionnaires, interview questions, observational tool, etc.).

The study member will screen for potential subjects using the UCIMC surgical schedule. If a subject is deemed ineligible based on the inclusion and exclusion criteria after reviewing the medical history, his/her record will be discarded. No records will be retained from ineligible subjects. After discussing with the patient's surgeon, study team member will initiate the informed consent process by approaching each eligible subject to explain the study and what it entails. The Lead Researcher will address all questions and concerns from the subject before asking the subject to sign the research consent form.

The GE anesthesia machines currently owned by the operating room will be used to serve as the comparator to the Flow-i machine. The high volume anesthesia machines do not use a low volume system. Subjects will be randomized by recruitment day. On a given recruitment day, all consented subjects will receive anesthesia from one of two groups:

- (1) MAQUET FLOW-i device
- (2) GE anesthetic device

Time points for both groups include:

T₀: Time of intubation, when volatile anesthetic are typically first delivered to the patient. We will use 15L/min fresh gas flow, while dictating tidal volumes of 6-8 mL/kg ideal body weight and a PEEP of 6 centimeters of water (cm H₂O) in accordance with current best practices.

T₁: Time of incision, which typically represents the time of reaching steady state conditions of volatile anesthetic delivery. We will reduce fresh gas flow to 2 L/min in accordance with local practice and weigh the vaporizer at this point, allowing us to measure comparative anesthetic consumption during this wash-in time period (T₀-T₁).

T₂: Time of anesthetic weaning, typically the time when preparing for patient emergence begins by discontinuing the delivery of volatile anesthetics to the patient. The vaporizer will be re-weighed at this point, allowing us to measure comparative anesthetic consumption at steady state maintenance of anesthetic depth (T₁-T₂)

Logically, we will also be able to use T₀-T₂ in order to understand total comparative anesthetic consumption.

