Note: Compensation should be offered on a prorated basis when the research involves multiple sessions.

Not applicable - This study involves no interaction/intervention with research subjects (i.e., involves the use of records, charts, biospecimens).

No compensation will be provided to subjects.

No reimbursement will be provided to subjects.

SECTION 12: CONFIDENTIALITY OF RESEARCH DATA

1. Indicate all identifiers that may be included in the research records for the study. Check all that apply:

Note: If this information is being derived from a medical record; added to a medical record; created or collected as part of health care, or used to make health care decisions it qualifies as PHI under HIPAA. The subject's HIPAA Research Authorization is required or a waiver of HIPAA Authorization must be requested (Appendix T).

No subject identifiers are obtained (i.e., researchers will not collect information that can link the subjects to their data)

OR

 Names	 Social Security Numbers	 Device identifiers/Serial numbers
 Dates*	 Medical record numbers	 Web URLs
 Postal address	 Health plan numbers	 IP address numbers
 Phone numbers	 Account numbers	 Biometric identifiers
 Fax numbers	 License/Certificate numbers	 Facial Photos/Images
 Email address	 Vehicle id numbers	 Any other unique identifier

Other (Specify all): *<Type here>*

* birth date, treatment/hospitalization dates

2. Explain how data will be **recorded**.

Check all that apply:

Paper documents/records
 Electronic records/database
 Audio recording
 Video recording
 Photographs
 Biological specimens
 Other(s) (specify):

3. Indicate **how data will be stored, secured** including paper records, electronic files, audio/video tapes, biospecimens, etc.

Note: If the research data includes subject identifiable private information and/or Protected Health Information, the storage devices or the electronic research files must be encrypted.

Electronic Data (check all that apply):

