Coded data; code key is kept separate from data in secure location.

Data includes subject identifiable information. **Note: Encryption software is required.** (Provide rationale for maintaining subject identifiable info):

Data will be stored on secure network server.

Data will be stored on stand alone desktop computer (not connected to network/internet)

Other (specify here):

Hardcopy Data, Recordings and Biospecimens (check all that apply):

Coded data; code key is kept separate from data in secure location.

Data includes subject identifiable information (Provide rationale for maintaining subject identifiable info):

We will only maintain subject identifiable for organization purposes only. Access to this information is limited to only study team members at UCIMC and must be approved by the lead researcher. All data will be de-identified before study team conducts any statistical tests, sharing data with MAQUET for research purposes.

Data will be stored in locked file cabinet or locked room at UCI/UCIMC.

Data will be stored locked lab/refrigerator/freezer at UCI/UCIMC.

Other (specify here):

Data on Portable Devices:

4. Describe the **portable device(s) to be used** (e.g. laptop, PDA, iPod, portable hard drive including flash drives).
5. Specify whether **subject identifiable data** will be stored on the device. If so, **justify why** it is necessary to store subject identifiers on the device.

Note: Only the “minimum data necessary” should be stored on portable devices as these devices are particularly susceptible to loss or theft. If there is a necessity to use portable devices for initial collection of identifiable private information, the portable storage devices or the research files **MUST BE ENCRYPTED**, and subject identifiers transferred to a secure system as soon as possible.

Not applicable – No study data will be maintained on portable devices.

Data Access:

6. Specify who, besides the entities listed below, will have **access to subject identifiable private data and records**.
7. If there is a **code key**, specify who on the research team will hold the key, and who will have access to the key.
8. If publications and/or presentations will include **subject identifiable information**, specify where the data will be **published and/or presented** and address how the study team will obtain permission from subjects.

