Note: Authorized UCI personnel such as the research team and the IRB, the study sponsor (if applicable), and regulatory entities such as the Food and Drug Administration (FDA) and the Office of Human Research Protections (OHRP), may have access to study records to protect subject safety and welfare. Any study data that identifies the subjects should not be voluntarily released or disclosed without the subjects' separate consent, except as specifically required by law. Publications and/or presentations that result from this study should not include subject

identifiable information; unless the subject's separate consent has been obtained.

Not applicable – No subject identifiers will be collected.

Not applicable – Only the entities listed above will have access to subject identifiable private data and records.

Only approved study team members at UCIMC will have access to identifiable information for research purposes only. The lead investigator will hold the code key and will only distribute to study team members when deemed appropriate.

Data Retention:

9. Explain **how long subject identifiable research data will be retained**. The data may include a code with a separate code key or the data may include subject identifiers.

Notes:

- *If more than one of the options below is applicable [e.g., the study involves children], records should be kept for the longer period.*
- *Research documentation involving Protected Health Information (PHI) should be retained for six years (e.g., IRB documentation, consent/assent forms – NOT the actual PHI). Investigators must destroy PHI at the earliest opportunity, consistent with the conduct of this study, unless there is an appropriate justification for retaining the identifiers or as required by law.*

Not applicable. No subject identifiable research data will be retained.

Destroy once data collection is completed

Destroy at the earliest opportunity, consistent with the conduct of this research. Specify timeframe: [*<Type here>*](#)

Destroy after publication/presentation

Maintain for approximately [*<six>*](#) years. (e.g., 3 months, etc.)

Maintain in a repository indefinitely. Other researchers may have access to the data for future research. Any data shared with other researchers, will not include name or other personal identifying information. Note: [*Appendix M is required.*](#)

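### The machine is allocated by recruitment day, but the only stated test ignores day, and the plan does not say that a coded day stays in the de-identified file

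*Combined protocol and SAP*

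**What the plan says.** **Allocation.** The study procedures in Section 3 state: "Subjects will be randomized by recruitment day. On a given recruitment day, all consented subjects will receive anesthesia from one of two groups". The randomized unit is the day, and everyone consented on a day is in the same arm.

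**Analysis.** The only comparison named is in the sample-size text of Section 3.B: a one-sided t-test at the 5% level with 55 patients per group. No day term or day-level variance appears there or elsewhere.

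**Data handling.** Section 12, item 1 ticks dates as an identifier, and its footnote reads "birth date, treatment/hospitalization dates". The hardcopy-data paragraph of the same section says "All data will be de-identified before study team conducts any statistical tests, sharing data with MAQUET for research purposes".

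**The code key.** Under Data Access, "The lead investigator will hold the code key and will only distribute to study team members when deemed appropriate". The storage options include "Coded data; code key is kept separate from data in secure location", but the available text does not show whether that box was ticked.

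The plan does not say that a coded recruitment day is kept in the de-identified file. It does not say that one is removed.

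**The concern.** When days are randomized, patients treated on the same day are not independent replicates of the allocation. They may also share features that affect agent consumption, such as operating list, staff and case mix. A t-test that counts patients as independent then tends to understate the standard error of the difference between machines. The p-value is too small and the confidence interval too narrow.

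The data-handling text adds a second, smaller difficulty. A day-clustered standard error needs a variable showing which patients shared a day. The treatment date is the obvious link, but the plan classes it as an identifier and calls for de-identification before any test and before sharing with the manufacturer. No substitute variable is mentioned.

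At stake are the validity of the primary comparison and the ability of anyone holding only the de-identified file to correct it. The record of allocated against used machine also matters. Clinicians are not blinded, and Sections 3.B and 4.A foresee excluding subjects because another machine was used. Such an exclusion can be judged only against the machine assigned to that day.

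**Working it through.** **1. The plan's own figure.** Inputs from Section 3.B: cost per case 9.6 against 7.2 dollars, so a difference of 2.4; SD 5.0 in both groups; one-sided alpha 0.05; power 0.80.

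- Normal approximation: n per arm = 2 × (1.645 + 0.842)² × 5.0² / 2.4² = 2 × 6.185 × 25 / 5.76 = 53.7, so 54.
- Exact t calculation: 54.36, so 55.

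The stated 55 per arm reproduces. A two-sided test would need 69 (normal) or 70 (t) and does not match. The calculation treats patients as independent.

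**2. What ignoring day does.** The documents give neither the number of subjects per day (m) nor the within-day correlation (ICC). The values below are assumptions: m from 2 to 4, equal across days, and ICC from 0.05 to 0.20.

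- Design effect: DE = 1 + (m − 1) × ICC.
- Actual size of the nominal 5% one-sided test: 1 − Φ(1.645 / √DE).
- Approximate power of an analysis that allows for day, at 55 per arm: the plan's power formula with 55 / DE patients per arm.

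| m | ICC | DE | Actual size when day is ignored | Power allowing for day |
|---|---|---|---|---|
| 1 | any | 1.00 | 5.0% | 0.808 |
| 2 | 0.05 | 1.05 | 5.4% | 0.791 |
| 2 | 0.20 | 1.20 | 6.7% | 0.743 |
| 3 | 0.10 | 1.20 | 6.7% | 0.743 |
| 4 | 0.10 | 1.30 | 7.5% | 0.713 |
| 4 | 0.20 | 1.60 | 9.7% | 0.635 |

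Last row written out: DE = 1 + 3 × 0.20 = 1.60; 1.645 / √1.60 = 1.300; upper tail 0.0967.

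**3. Effect on precision.** The interval widens by a factor √DE: √1.05 = 1.02 to √1.60 = 1.26. Degrees of freedom would come from days. With 110 subjects, 2 per day gives 110 / 2 = 55 days and 55 − 2 = 53 degrees of freedom; 4 per day gives about 28 days and 26. The patient-level test uses 110 − 2 = 108.

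**4. Does the day survive de-identification?** No arithmetic applies. Section 3 makes the day the randomized unit. Section 12 treats the calendar date as an identifier and de-identifies before testing and sharing. A sequential number (day 1, day 2 and so on) is not a calendar date, so de-identification permits it, but nothing requires it. The key lets the site recover the date. The plan gives no key access to anyone outside the study team.

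**The case against.** A reader might infer that Section 12 strips the randomization unit from the analysis file, so that the standard error could never be corrected or audited. The case against that reading is strong.

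- **No removal is stated.** De-identification does not require dropping an arbitrary day number, so the loss is an inference.
- **The site keeps the link.** The lead investigator holds the key and may release it to the study team, who could recover the day and reanalyse.
- **The list of recorded variables is not a dataset specification.** It is introduced as an addition to the vaporizer weighings and omits the group label as well. The absence of a day field from it proves nothing. The data collection instruments are not part of the documents.
- **The group label carries much of the allocation.** Everyone on a day has the same machine, and the plan expects the team to notice use of a different device.
- **The inflated error is not due to de-identification.** It would be the same with every calendar date left in the file.

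All of this stands, and it limits the data-handling part to a missing assurance. It does not answer the main point: the allocation is by day and the stated test is not. Release of the key is also discretionary and confined to the study team, so it does not help the manufacturer or any other recipient. Nor does the plan say whether the group label records the machine allocated or the machine used.

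**Conclusion.** The point holds in a limited form. The stated test does not match the unit of allocation, and the plan neither specifies a day-respecting analysis nor ensures that the de-identified file would support one. The documents do not show that the day is removed or that the site would be unable to correct its own analysis; only a recipient without the key would be.

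The size is conditional. A nominal 5% one-sided test would run at about 5.4% to 9.7% if there are 2 to 4 subjects per day and the within-day correlation is 0.05 to 0.20. With one subject per day, or no within-day correlation, there is no inflation. The whole of this effect belongs to the t-test in Section 3.B and none of it to the confidentiality text in Section 12.

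**What to change.** 1. In Section 3.B, state that the standard error, confidence interval and test for the primary variable will be computed with recruitment day as the cluster, with degrees of freedom based on the number of days.
2. In Section 12, add one sentence: before dates are removed, each recruitment day receives a sequential study-day number, and the de-identified analysis and shared files keep that number, the machine allocated to the day and the machine actually used.
3. Report a table of allocated against used machine.

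This needs three coded fields and two short text changes. It adds no subjects or procedures and retains no calendar date. The price is a somewhat wider interval and fewer degrees of freedom, and under the assumed values power at 55 per arm would be about 0.79 down to 0.64 instead of the planned 0.80. That loss comes from allocating by day. The patient-level test does not avoid it; it only leaves it out of the reported standard error.
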